6.3 Population / Sample size including power calculation

Sample size:

The sample size will be 20 children, 10 in each group.

Sample size calculation:

Sample size calculator used: https://www.ai-therapy.com/psychology-statistics/sample-size-calculator)

This pilot RCT is the first to use ReST with children with CP in a randomised controlled trial. There are no previous studies of this intervention with this population using the proposed outcome measures from which sample sizes could be calculated, so studies with similar populations, treatments, and measures were considered for sample size calculations. ReST is a motor speech intervention for the treatment of childhood apraxia of speech (CAS). While it has been shown to be effective in improving speech in children with CAS, it has not been researched with children with CP. Our exploratory pilot study on the use of ReST with children with CP indicated improvement in mean length of utterance, with a d2 effect size of 0.56. This effect size gives a sample size of 6. This was derived from calculating the effect sizes from the group means (baseline and maintenance), and standard deviation for four outcome measures. Speech MLU is a secondary outcome in the current study ReST effect sizes have primarily been calculated using d2. Using this metric, Thomas (2017) reported an average ReST intervention effect size of 5.55 (SD 2.41, range 2.48-8.52). (Previously published single-case clinician-delivered ReST treatment studies reporting similar dependent measures; McCabe et al., 2014; Thomas et al., 2014; Thomas et al., 2016). Using this effect size with a power of 0.8 and alpha of 0.05 the online sample size calculation produced a sample size of **3 for each group**. The only other RCT using ReST in children with CAS produced an effect size (Cohen's d) of 1.376 giving a sample size of 10 for each group.

The other motor speech interventions used with children with CP include LSVT LOUD (Boliek & Fox, 2017), Speech Systems Intelligibility Treatment (Pennington et al., 2010; 2013), and PROMPT (Ward, 2012). Sample size calculations were derived for each of these studies.

LSVT LOUD: Boliek & Fox, 2017 reported a Cohen's d effect size of 0.3 for pre and post speech intelligibility measures. The sample size calculation was therefore a sample size of 52.

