6.7 Participant Withdrawal

Participants will be informed in the Participant Information Statement about their right to withdraw at any time. If the participant wishes to withdraw, they are asked to inform the study coordinator or another of the investigators. At this point, parents will be asked if they wish the researchers to retain or destroy already collected data. If the participant agrees, then their data will be retained and analysed using intention to treat analysis. If the participant does not agree, then their data will be destroyed. Parents who decide to withdraw from the research will be asked for their reasons and these will be recorded and reported if they are provided and if consent is provided.

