6.7.2 Handling of withdrawals and losses to follow-up

Intention to Treat (ITT) will be used to statistically analyse the results if there is loss to follow up, or if there are any deviations from the original assigned groups.

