6.14 Statistical analyses

Data analysis will utilize repeated measures ANOVA and Cohen's d effect sizes to compare the treatments over time.

Repeated measures ANOVA (2 groups x 6-time points) will be run for the primary and secondary outcome measures.

If there is any attrition, an intention-to-treat analysis will be conducted.

For statistically significant comparisons, Cohen's d effect sizes will be calculated (Cohen, 1988).

7. ETHICAL CONSIDERATIONS (see data, section 10 for privacy and confidentiality) 7.1 Potential Risks and Proposed Benefits

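### The only named model, repeated-measures ANOVA, excludes children with a missing visit unless values are imputed, and the protocol gives them no route into the promised intention-to-treat analysis

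*Protocol*

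**What the plan says.** Protocol section 6.14 fixes the model: "Repeated measures ANOVA (2 groups x 6-time points) will be run for the primary and secondary outcome measures". In the same section, the provision for attrition is: "If there is any attrition, an intention-to-treat analysis will be conducted".

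Two other places make the same promise. Section 6.7.2 states: "Intention to Treat (ITT) will be used to statistically analyse the results if there is loss to follow up"; the sentence goes on to cover departures from the assigned groups as well. Section 6.7 says of withdrawn children: "If the participant agrees, then their data will be retained and analysed using intention to treat analysis". It also says: "If the participant does not agree, then their data will be destroyed".

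On size, section 6.3 states: "The sample size will be 20 children, 10 in each group". It raises the figure from six to ten per group partly as an allowance for attrition, and section 6.7.3 rules out replacing children who withdraw. No attrition rate is given anywhere.

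No section says how a child with some visits missing enters the ANOVA.

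**The concern.** Intention-to-treat settles who is analysed and in which group. It does not say what to do when an outcome value is absent. The protocol uses it as the remedy for missing data, while the model it names handles missing data by leaving the child out. A child assessed at T1 to T4 who misses T5 would lose every value, including T2 and T3, which carry the only comparison of ReST with usual care before the usual-care group starts ReST.

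Two things are at stake. The first is precision, in a trial of 20 children with no replacement. The second is bias, if missing a visit is related to progress, fatigue or allocation. That is plausible here: treatment is unblinded, and section 6.7.1 has families who cannot follow the treatment protocol advised to discontinue.

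**Working it through.** **Inputs from the protocol**
- 10 children per group (6.3).
- Sizing basis for ten per group: the ReST trial in childhood apraxia of speech, which "produced an effect size (Cohen's d) of 1.376 giving a sample size of 10 for each group".
- Power 0.8 and alpha 0.05 (6.3). Sidedness is not stated; two-sided is assumed.
- Post-baseline visits T2, T3, T4 and T5 (6.2). Section 6.14 counts six time points although 6.2 schedules five assessments. That is a separate inconsistency on which this point does not depend.
- Follow-up length: 6 weeks of treatment + 3 weeks to T3 + 6 weeks of treatment + 3 weeks to T5 = 18 weeks, before any scheduling gaps.

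**Step 1: reproduce the protocol's figure.** Two-sided two-sample t test at d = 1.376 and alpha 0.05. With n1 and n2 children, the noncentrality is d × √(n1·n2/(n1+n2)) on n1+n2−2 degrees of freedom. At 10 v 10 this is 1.376 × √5 = 3.08 on 18 df, giving power 82.9%. At 9 v 9 power is 78.2%, below 80%. The stated 10 per group therefore reproduces.

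**Step 2: how the model treats a missed visit.** A simulated set of 20 children by 5 visits (100 values) had one value deleted. A standard repeated-measures ANOVA routine rejected the data as unbalanced, so the child must be removed or the value imputed. A linear mixed model fitted the same data with all 20 children and 99 observations.

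**Step 3: complete cases.** Let m be the assumed chance that a child misses any one visit, independently across T2 to T5. The share of children with complete data is (1 − m)^4.

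| m (assumed) | (1 − m)^4 | complete, of 20 |
|---|---|---|
| 2% | 0.922 | 18.4 |
| 5% | 0.815 | 16.3 |
| 10% | 0.656 | 13.1 |
| 15% | 0.522 | 10.4 |

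If the same children miss several visits, as happens after withdrawal, the same per-visit rate leaves more complete cases than this.

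**Step 4: power at the reduced sizes** (same t test, d = 1.376)

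| complete children | power |
|---|---|
| 10 v 10 | 82.9% |
| 9 v 9 | 78.2% |
| 8 v 8 | 72.6% |
| 6 v 7 | 61.6% |

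These sizes correspond roughly to no loss and to the 2%, 5% and 10% rows of Step 3. The t test matches the protocol's own sizing method. It is only a proxy for the planned group-by-time ANOVA.

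**The case against.** The strongest reply is that the protocol never says incomplete children are deleted. Sections 6.7 and 6.7.2 point the other way, since retained data of withdrawn children are to be analysed. An ANOVA on imputed data can include every randomised child, and an imputation rule is the kind of detail often left to a statistical analysis plan, which may exist. This stands in part. A reader might infer that the planned method cannot deliver intention-to-treat at all; that is true only without imputation. What survives is that the protocol itself fixes both the model and the attrition promise, and the two do not fit together as written.

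A reader might also infer that making intention-to-treat conditional on attrition is a fault that alters the result. The documents do not support that. Section 6.7.2 also invokes it for departures from the assigned groups. If neither loss nor departure occurs, every child is complete and in the allocated group, so the two analyses coincide. The wording is untidy and no more.

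Finally, the losses rest on assumed rates, and ten per group already includes some attrition allowance. Both are fair. One withdrawal per group leaves 9 v 9 and 78% power, a modest loss. The allowance does not protect the effect size cited for ten per group, however: at d = 1.376 all ten are needed to exceed 80%. Nor does any allowance address selection bias among completers.

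**Conclusion.** The point holds in this form: the one model named excludes any child with a missing visit unless values are imputed, the protocol supplies no imputation or other route, and so, followed as written, the analysis is of completers. That contradicts the intention-to-treat promise made in 6.7, 6.7.2 and 6.14.

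The exclusion is a property of classical repeated-measures ANOVA, not something the protocol states. The size is illustrative: about 18 down to 10 of 20 children complete for assumed independent miss rates of 2% to 15% per visit, with proxy power falling from 83% to 62% by the 10% rate. The direction and amount of any bias cannot be judged from the document. The change should be made, but the documents do not show that the trial is already compromised.

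**What to change.** In section 6.14, replace the repeated-measures ANOVA with a likelihood-based mixed model for repeated measures:
- categorical visit and the group-by-visit interaction;
- T1 either as a covariate or as part of the outcome vector;
- child as the subject;
- REML estimation with Kenward-Roger degrees of freedom;
- all available visits of randomised children, in their allocated group;
- the randomised phase-1 contrast (T2/T3) as the target, because both groups have received ReST by T4.

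State this as the analysis in all cases and align 6.7 and 6.7.2 with it, which also tidies the conditional wording.

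The cost is a few sentences and standard software, with no extra children or visits. The model assumes data are missing at random. It cannot recover children whose data are destroyed at the family's request. With T1 as a covariate, a child with no post-baseline visit contributes nothing. Keeping the ANOVA with a pre-specified imputation rule would also remove the contradiction, but the mixed model uses the observed visits directly.

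### Cohen's d is to be calculated for statistically significant comparisons, which biases the reported effect sizes upward on average and leaves non-significant outcomes without one

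*Protocol*

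**What the plan says.** Protocol section 6.14 opens with a general statement: "Data analysis will utilize repeated measures ANOVA and Cohen's d effect sizes to compare the treatments over time". It then names the model: "Repeated measures ANOVA (2 groups x 6-time points) will be run for the primary and secondary outcome measures". It closes with the rule at issue: "For statistically significant comparisons, Cohen's d effect sizes will be calculated". The section makes no provision for an effect size when a comparison is not significant. It also does not say which comparisons receive a d (between groups, within child, or change by group) or which standard deviation is the divisor.

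Section 6.3 sets the size of the trial: "The sample size will be 20 children, 10 in each group". It describes the trial's place in the evidence as follows: "This pilot RCT is the first to use ReST with children with CP in a randomised controlled trial". Under section 6.2 the usual care group starts ReST once the T3 assessments are done, so T2 and T3 are the post-baseline assessments at which the randomised groups differ in having received ReST.

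**The concern.** An estimate that is shown only when it passes a significance test is not a fair sample of the estimates the trial could have produced. In a small trial the test is passed only by large observed effects. The effect sizes that survive are therefore too large on average, and the outcomes that fail have no effect size at all.

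This matters more here than in a large confirmatory trial. Section 6.3 notes that no earlier study of ReST in this population used these outcome measures in a way that could support a sample size, and it builds its own case from published effect sizes. For two earlier studies the investigators had to compute d themselves because none had been reported. A later team will probably turn to this trial for the same purpose. It would find inflated values for some outcomes and none for others.

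**Working it through.** **Inputs.** From section 6.3: 10 children per group, alpha 0.05, power 0.8, and a planning effect given as "produced an effect size (Cohen's d) of 1.376 giving a sample size of 10 for each group". Also from section 6.3, as illustrative true effects: 0.3 (a pre-post d for intelligibility from a voice-treatment study in cerebral palsy) and 0.56 (from the exploratory ReST pilot, which "indicated improvement in mean length of utterance, with a d2 effect size of 0.56"). The value 0.8 is not in the protocol and is added to fill the range. The protocol does not state sidedness, so two-sided testing is assumed. It gives no within-child correlation, so a range of 0.5 to 0.9 is assumed.

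**Step 1: reproduce the plan's figure.** For a two-sample t-test with d = 1.376 and two-sided alpha 0.05, the noncentral t distribution gives power 0.782 with 9 per group and 0.829 with 10. The smallest n reaching 0.8 is 10, as the protocol says. One-sided testing would give 8, so the stated figure fits the two-sided reading.

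**Step 2: smallest significant d between groups.** Because t = d × √(n/2), the threshold is t(0.975, 2n − 2) × √(2/n). With n = 10 this is 2.101 × 0.447 = 0.94. One-sided it would be 0.775. With attrition to 9 or 8 per group, the two-sided threshold rises to 1.00 or 1.07.

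**Step 3: smallest significant d within child.** Write dz for the mean change divided by the SD of the change. Then t = dz × √n.
- 10 children: 2.262 / 3.162 = 0.715
- 20 children: 2.093 / 4.472 = 0.468

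If d is scaled by the raw SD instead, these are multiplied by √(2(1 − r)). That factor is 1 at r = 0.5 and 0.447 at r = 0.9, so the ranges are 0.72 to 0.32 for 10 children and 0.47 to 0.21 for 20. A between-group difference in change, scaled by the raw SD, has a threshold of 0.94 to 0.42 over the same range of r.

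**Step 4: size of the bias in the between-group case.** For each true d, 200,000 trials of 10 v 10 were simulated with normal outcomes and equal SDs. d was kept only when p < 0.05 (two-sided).

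| True d | Share significant | Mean d, all trials | Mean absolute d, significant trials | Ratio to truth | Significant d at or below truth |
|---|---|---|---|---|---|
| 0.3 | 10% | 0.32 | 1.20 | 4.0 | 0% |
| 0.56 | 22% | 0.59 | 1.25 | 2.2 | 0% |
| 0.8 | 40% | 0.84 | 1.32 | 1.65 | 0% |
| 1.376 | 83% | 1.44 | 1.59 | 1.15 | 38% |

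The third column shows that, without the filter, the mean d is close to the truth, with only a small-sample excess of about 4 to 5%. At 1.376 that excess is part of the 15%: 1.437 / 1.376 = 1.04 arises without any filter, and 1.589 / 1.437 = 1.11 comes from the filter. At a true d of 0.3, the ratio of 4.0 is for absolute size. Some significant results then have the wrong sign, and the signed mean is 1.085, or 3.6 times the truth.

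**Step 5: how often no d is calculated.** This is one minus the share significant: about 90%, 78%, 60% and 17% of trials for the four rows.

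**The case against.** The best defence is textual. The opening sentence of section 6.14 uses d with no condition, and the closing sentence does not contain the word 'only'. Nothing says that group means and SDs will be withheld, so a reader could often compute a d. This has some force: a missing d is not the same as a missing result. But the closing sentence is the only one that says when d is calculated, and it names significant comparisons alone. If the opening sentence is meant to govern, the closing one contradicts it and still needs to be changed.

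A second objection concerns reach. A reader might infer that every d this trial reports will be at least 0.94. The protocol does not support that. The design is a cross-over analysed by repeated measures ANOVA, so within-child and change contrasts may be among the comparisons, and these can be significant at much smaller values (step 3). The figure of 0.94 belongs to a two-sided between-group comparison with 10 per group.

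A third objection concerns size. A reader might infer that each reported d will overstate the truth. That is guaranteed only if the true between-group d is below 0.94. At the planning value of 1.376 the average inflation is about 15%, and 38% of significant values do not exceed the truth. Also, 0.56 is a d2 figure for mean length of utterance and 0.3 is a pre-post figure. Neither is a between-group d for ReST against usual care, so the 2.2-fold and 4.0-fold ratios are illustrations and not forecasts.

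Finally, it would go too far to say that the next trial will be undersized, or that the effect sizes cited in section 6.3 were themselves selected on significance. The protocol says neither, and the cited values include 0.3 and −0.5.

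**Conclusion.** The point stands in a limited form. As written, the rule ties calculation of d to the p-value, sits uneasily with the same section's opening sentence, biases the reported d upward on average, and leaves non-significant outcomes without a d. The direction of the bias does not depend on which contrast is used; its size does. The ratios in step 4, from 1.15 at the planning effect to 4.0 at a true d of 0.3, rest on two-sided testing at 0.05, a simple two-group comparison of 10 v 10, normal outcomes with equal SDs and no attrition.

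The hypothesis tests are unaffected. What suffers is the effect estimate that later researchers are likely to reuse, so the text should be changed, although the flaw does not invalidate the trial.

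**What to change.** Replace the last sentence of section 6.14 with:

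> For every primary and secondary outcome, the between-group difference and Cohen's d (standardiser stated), each with a 95% confidence interval, will be reported whatever the p-value, for the randomised comparison before the usual care group starts ReST (T2 and T3). Any other planned contrast will be reported in the same way.

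This removes the filter and agrees with the section's opening sentence. It also ties the main effect size to the assessments made before the control group crosses over. It needs no additional children, visits or measurements; the cost is a few extra table rows.

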7.1.1 Potential Risks

This is a relatively low-risk project and does not pose foreseeable risks to the participants or their families. The speech pathology involvement is not different from the usual speech pathology practice but may involve mild distress from time to time as tasks may be difficult for the child.

As this is a trial study of ReST with children with CP, there is a risk of no improvement in speech intelligibility or communicative participation at the end of the study. The families are informed of this at recruitment.

Participants receive treatment from speech pathology students. There is a small risk that the students' inexperience may impact on the intervention quality or the ability to recognise subtle signs of participant fatigue, however previous ReST studies involved speech pathology students successfully in the treatment delivery, including McCabe, et. al (2014) and Murray, et. al. (2015) studies. Students will be supervised by the research team members and will receive guidance and support to maintain a high standard of service delivery and participant care.

Privacy and confidentiality pose a risk. This is covered in section 9 Data Management.

7.1.2. Participant Benefits

The participants will not be disadvantaged by randomisation as both groups will receive the ReST intervention and all the assessments.

7.2 Responsibility for liability of injury

The participants may experience fatigue and frustration during assessments or treatment. The supervising speech pathologists and the speech pathology students will be instructed to note signs of fatigue or frustration and to give the child a short break if these occur. The students are covered by University of Sydney insurance for clinical placements. The WHS requirements for risk minimization will be adhered to throughout the study intervention. A covid-safe protocol is attached.

7.3 Recruitment

Recruitment will take place from CP Alliance therapy and via the NSW CP register. Potential participants are directed to contact the study coordinator. The research team or the student speech pathologists will not approach or contact the potential participants.

7.3.1. Dual or unequal relationship, potential for coercion or inducement

The participants are protected against potential coercion in that they are not approached directly by any of the research team members.

Participants are also informed that if they decline to participate or withdraw from the study, this will not effect their relationship with the research team, The University of Sydney, or Cerebral Palsy Alliance.

7.4 Informed Consent

The participants are informed about the study and given the PCF and the PIS. The family can choose whether they want to sign the consent form. If the family declines to participate in the study, they are assured that this will not impact their relationship with the research team members, The University of Sydney, or Cerebral Palsy Alliance and its staff. The family is provided the name and contact details of the PI and the study coordinator if they require further information. They are also provided the contact details of the University of Sydney ethics committee if they have any concerns or complaints about the study.

The families are informed that their participation is completely voluntary. They are free to decline to attend the study, and also free to withdraw from the study at any time. This will have no implications on their relationship with the research team, the University of Sydney, or Cerebral Palsy Alliance.

8. SAFETY CONSIDERATIONS

8.1 Assessment and Documentation of Adverse Events

To ensure consistent procedures and safety of the participants, the participants' progress and will be monitored. Speech pathologists in the research team will supervise the speech pathology students who deliver the treatment. This includes monitoring the maintenance of accurate delivery of ReST treatment and to ensure the participants' experiences during the treatments are positive. The supervisor provides feedback and support during and after the treatment sessions. Adherence to the treatment protocol and participants' experiences are discussed and adjustments are implemented where required.

Children who become distressed will be provided with a break, with encouragement, and with appropriate support in consultation with them and their parents. If the child and the parent consent to continuing, the session will recommence after a short break. Otherwise, the session will be discontinued.

Direct observation of the students occurs during the first four sessions of the treatment block. After this, the frequency of direct observation is gradually reduced to once a week, in line with usual practice. As all sessions will be recorded, the student and the supervisor can review the sessions where the supervisor was not present.

